Cochlear implantation has been reported as a viable treatment option in cases of unilateral hearing loss, including sudden sensorineural hearing loss (Firszt et al, 2012), and severe tinnitus (Vermiere & Van de Heyning, 2009; Van de Heyning et al, 2008). Further, cochlear implantation has been shown to offer superior speech perception in noise, localization abilities, and subjective report in SSD cases as compared to CROS hearing aids and bone-conduction devices (Arndt et al, 2011). The limitation to this comparison, however, was the subjects had limited listening experience with the alternative treatment options (i.e. CROS hearing aids or bone-conduction device). Though other studies reported no difference in abilities with these technologies after 4 weeks of listening experience (Bosman et al, 2003), long-term duration of listening experience may influence speech perception and localization abilities. Considering this, a control condition of long-term users of current treatment options (i.e. bone-conduction devices) may provide a more accurate comparison with SSD cochlear implant recipients.

The primary goal of this project is to determine whether subjects with SSD experience an improvement in speech perception, localization, and quality of life with a cochlear implant as compared to an unaided listening condition. Secondary aims include: 1) a comparison of speech perception, localization, and quality of life outcomes in the study population to a SSD control group with long-term listening experience with a current treatment option (i.e. bone-conduction device), and 2) a within-subject comparison of speech perception and localization abilities with cochlear implantation versus the bone-conduction test device.

III. Objectives

- A. The primary purpose of this feasibility study is to demonstrate the effectiveness of cochlear implantation in subjects with SSD
 - 1. Postoperative results will be evaluated with speech perception measures, localization tasks, and subjective reports

- B. Compare outcomes of cochlear implantation to that of current treatment options (i.e. bone-conduction devices) for SSD cases
 - 1. Compare speech perception, localization, and subjective outcomes to a control group of implantable bone-conduction device recipients
 - 2. Assess cochlear implant subjects with a bone-conduction test device and/or previous BAHA device at the preoperative and 12 month follow-up intervals

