The MAESTRO 6.0 Fitting Software will be used to program the Opus 2 speech processor. The MAESTRO 6.0 software, which is used for different intraoperative and postoperative purposes for the MED-EL Cochlear Implant System. Currently, it contains the implant Telemetry and Fitting of the OPUS 1 or OPUS 2 processor, ART (Auditory nerve Response Telemetry) and ESRT (Electrically Evoked Stapedius Reflex Threshold), and Audiogram functions. The MAESTRO software is an external component of the MED-EL Cochlear Implant System and is intended to be used in a clinical or office environment by persons adequately skilled and trained to perform all intended tasks and with patients who received one of the intended MED-EL cochlear implants.

VI. Study Duration

- A. Enrollment Period
 - 1. 4 years

B. Study Timeline

- 1. Cochlear implant subjects
 - a. Each subject's involvement will last approximately 1.5 years, including: candidacy evaluation, preoperative evaluation, surgical procedure, initial activation of the external speech processor, and post-initial activation evaluations (1, 3, 6, 9 and 12-months post-initial activation)
- 2. Bone-conduction device control group
 - a. One evaluation interval to complete the test battery outlined in section VII.D.

C. Study Endpoint

- 1. Cochlear implant subjects
 - a. The 12-months post-initial activation interval
- 2. Bone-conduction device control group
 - a. Completion of the test battery (1 interval) defined in section VII.D.

VII. Methods

All procedures will be conducted by UNC investigators, including board-certified otologists, audiologists, and speech-language pathologists. Fully informed consent will be obtained from all subjects.

A. Participants: CI subjects

Subjects must meet the following inclusion criteria and not exhibit any of the exclusion criteria.

- 1. Inclusion Criteria
 - a. Unilateral moderate-to-profound sensorineural hearing loss
 - i. Unaided residual hearing thresholds measured from 250-8000 Hz (PTA ≥70 dB HL in the ear to be implanted)
 - ii. Normal to mild residual hearing thresholds from 250-8000 Hz in the contralateral ear (≤35 dB HL at each frequency, 250-8000 Hz)
 - b. Greater than or equal to 18 years of age at implantation
 - c. Duration of moderate-to-profound sensorineural hearing loss less than or equal to 5 years
 - i. Either reported by subject or documented in previous audiograms

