 - ii. Can be less than or equal to 10 years if the subject consistently utilized hearing technology (such as a bone conduction device or conventional hearing aid) within the past 5 years
 - d. Previous experience with a current treatment option for SSD, including a conventional hearing aid, bone-conduction device, or CROS/BICROS technology.
 - i. At least one month of listening experience with device
 - ii. Dissatisfaction with and/or discontinued use of current treatment option due to: insufficient gain, poor sound quality, and/or lack of perceived benefit.
 - e. Aided word recognition in the ear to be implanted of 60% or less as measured with CNC words (50-word list)
 - i. When listening with an appropriately fit hearing aid and masking applied to the contralateral ear
 - ii. Aided testing will be conducted in a sound-proof booth with the subject seated 1 meter from the sound source, facing 0° azimuth. Recorded materials will be presented at 60 dB SPL.
 - iii. The hearing aid output will be measured using NAL-NL1 targets.
 - f. Realistic expectations: a verbal acknowledgement of the potential benefits and risks, and postoperative variation in performance. For instance, cochlear implantation will not restore normal hearing
 - g. Willing to obtain recommended meningitis vaccinations per CDC recommendations
 - h. No reported cognitive issues
 - i. Pass the Mini Mental State Examination (MMSE) screener
 - i. Able and willing to comply with study requirements, including travel to investigational site and study-related activities
- 2. Exclusion Criteria
 - a. Non-native English speaker
 - i. Speech perception materials are presented in English
 - b. Conductive hearing loss in either ear

- c. Compromised auditory nerve, including those with a history of vestibular schwannoma
- d. Ossification
- e. Inability to participate in follow-up procedures (i.e., unwillingness, geographic location)
- f. History of meningitis, autoimmune disease, or any medical condition that contraindicate middle or inner ear surgery or anesthesia
- g. Meniere's disease with intractable vertigo
- h. Trauma that precludes inner ear surgery
- i. Case of sudden sensorineural hearing loss that has not been first evaluated by a physician
- j. Pregnancy
 - i. Subjects who are pregnant or become pregnant prior to surgery are excluded due to the potential risk of anesthesia to an unborn child.
 - a. Subjects who become pregnant after surgery may continue to participate in study procedures

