- k. Tinnitus as the primary purpose for seeking cochlear implantation
- 1. Subject obtains a severe or catastrophic score on the Tinnitus Handicap Inventory (Newman, Jacobson & Spitzer, 1996).
- 3. Enrollment
 - a. This study seeks to enroll twenty (20) subjects
- B. Participants: Control group

Subjects must meet the following inclusion criteria and not exhibit any of the exclusion criteria.

- 1. Inclusion Criteria
 - a. Unilateral moderate-to-profound sensorineural hearing loss
 - i. Unaided residual hearing thresholds from 250-8000 Hz (PTA ≥70 dB HL on the implanted side)
 - ii. Normal to mild residual hearing thresholds from 250-8000 Hz in the contralateral ear ≤35 dB HL at each frequency, 250-8000 Hz
 - b. Recipient of bone-conduction device on affected side
 - i. Recipient of the Bone-Anchored Hearing Aid (BAHA)
 - a. Either the Cochlear BAHA Connect or Attract system
 - ii. At least 12 months of listening experience with the BAHA system
 - c. Greater than or equal to 18 years of age
 - d. Duration of moderate-to-profound sensorineural hearing loss less than or equal to 5 years at time of implantation with bone-conduction device (BAHA)
 - i. Either reported by the subject or documented in previous audiograms
 - e. Willingness to participate in test battery
- 2. Exclusion Criteria
 - a. Non-native English speaker

- i. Speech perception materials are presented in English
- b. Conductive hearing loss in either ear
- c. Compromised auditory nerve, including those with a history of vestibular schwannoma
- d. Inability to participate in test battery
- 3. Enrollment
 - a. This study seeks to enroll at least 10 subjects in the control group
- C. Timeline

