 - 1. Subjects will participate in two aural rehabilitation sessions with a board-certified speech-language pathologist. One session will be after the initial activation of the external speech processor. This will occur either on the same day as the initial activation or within the first 2 weeks of listening experience. The second session will be scheduled in conjunction with the 1-month post-initial activation interval.

VIII. Proposed Claims

- A. Demonstrate the effectiveness of cochlear implantation in SSD subjects
 - 1. Demonstrate an improvement in speech perception abilities, localization, and/or subjective benefit in an aided (cochlear implant on) versus an unaided (cochlear implant off) condition
- B. Cochlear implantation provides similar or superior speech perception, localization, and/or quality of life as compared to that found with bone-conduction devices
 - 1. Comparison with control group performance
 - 2. Comparison within subject when listening with bone-conduction test device

IX. Statistical Analysis

- A. Descriptive summaries will be provided for the following: subject demographics, and frequency of major and minor complications/adverse events.
- B. A single-subject design will be utilized, where each subject serves as his or her own control, for analysis of objective and subjective results. A single-subject design was chosen in order to accommodate the heterogeneity that is well known to characterize auditory prosthesis research. Repeated-measures ANOVA will be calculated with a p-value of ≤ 0.05 for statistical significance. Statistical analysis will be conducted with SPSS software.
 - 1. Comparison of aided speech perception performance on word and sentence materials in the post-initial activation intervals to evaluate trends over time

- a. Comparison of the difference between the aided and unaided conditions at each follow-up interval
- 2. Comparison of localization abilities in the post-initial activation intervals
 - a. Comparison of the difference between the aided and unaided conditions for each follow-up interval
 - b. Compute the overall rms error, random error, constant error, and adjusted constant error, as described by Grantham et al (2007)
- 3. Comparison of subjective report scores in the post-initial activation intervals

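### Implant subjects are screened for cognition and bone-conduction controls are not, so the secondary between-group comparison (Claim B.1) has an avoidable, unmeasured selection difference

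*Combined protocol and SAP*

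**What the plan says.** For implant subjects, VII.A.1.h asks for "No reported cognitive issues" and adds a test: "Pass the Mini Mental State Examination (MMSE) screener".

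For controls, VII.B.1 covers hearing thresholds in each ear, a BAHA used for at least 12 months, age, duration of loss and, last, "Willingness to participate in test battery". VII.B.2 excludes non-native English speakers, conductive loss, a compromised auditory nerve and "Inability to participate in test battery". Neither list has a cognitive item.

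Controls are seen once (VI.B.2): "One evaluation interval to complete the test battery outlined in section VII.D". That battery consists of audiometry, tympanometry, speech perception, localization and three questionnaires, with no cognitive test.

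The two groups meet in Objective III.B.1, "Compare speech perception, localization, and subjective outcomes to a control group of implantable bone-conduction device recipients", and in Claim VIII.B, "Cochlear implantation provides similar or superior speech perception, localization, and/or quality of life as compared to that found with bone-conduction devices", whose first support is "Comparison with control group performance". Section IX describes repeated-measures ANOVA with each subject as his or her own control. It gives no matching, covariate or other adjustment for the control comparison.

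**The concern.** Repeating words and sentences, particularly in noise, depends on attention and memory as well as on hearing. A criterion that removes people with cognitive problems from one group only can therefore make the groups differ for reasons unrelated to the device. Through this one factor, the effect on speech scores would be to lower the control group and so favour the implant.

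Two features of the plan make this worth closing. Claim B is framed as similar or superior with no margin stated, so even a small fall in control scores helps it. And the control group may be as small as 10, so one or two low scorers can move its mean. Because nothing cognitive is recorded in controls, the question could not be settled after the fact.

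**Working it through.** The plan states no figure on this point, so there is none to reproduce. The check has two parts.

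**1. Is the difference real, and does anything else close it?**

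- Both groups share the criteria that bear on test performance: thresholds in each ear, adult age, native English (justified in both lists by the language of the test materials), no conductive loss and no compromised nerve. Cognition is the performance-related item that appears for one group only.
- The control exclusion for inability to do the battery removes people who cannot perform the tasks. It does not remove people who can perform them but do so less well.
- Neither group has an upper age limit.
- Neither VII.D nor Section IX supplies a measurement or an adjustment.

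The difference stands and nothing else in the documents removes it.

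**2. How large could it be? (illustration only)**

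From the documents: 20 implant subjects with about 20% dropout allowed for, so 20 × 0.8 = 16 completers; at least 10 controls; significance at 0.05 (two-sided assumed). Assumed, because the documents give nothing: a share *f* of controls impaired, 0.1 to 0.3; a deficit *d* of 0.5 to 1.0 SD; equal SDs; a simple two-group comparison of means with a normal approximation.

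- Standard error of the difference: √(1/10 + 1/16) = 0.403 SD with 16 implant subjects; √(1/10 + 1/20) = 0.387 SD with 20.
- Difference detectable with 80% power, (1.960 + 0.842) × SE: 1.13 SD and 1.09 SD.
- Bias: *b* = *f* × *d*.
- Chance of a significant result favouring the implant when the devices do not differ: 1 − Φ(1.96 − *b*/SE), which is 0.025 when *b* = 0.

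| *f* | *d* (SD) | *b* (SD) | Chance, 16 implant | Chance, 20 implant |
|---|---|---|---|---|
| 0.1 | 0.5 | 0.05 | 0.033 | 0.034 |
| 0.1 | 1.0 | 0.10 | 0.043 | 0.044 |
| 0.2 | 0.5 | 0.10 | 0.043 | 0.044 |
| 0.2 | 1.0 | 0.20 | 0.072 | 0.074 |
| 0.3 | 0.5 | 0.15 | 0.056 | 0.058 |
| 0.3 | 1.0 | 0.30 | 0.112 | 0.118 |

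For the last row with 20 implant subjects: 0.30/0.387 = 0.775; 1.96 − 0.775 = 1.185; 1 − Φ(1.185) = 0.118.

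The chance that at least one of 10 controls is impaired is 1 − (1 − *p*)^10. At an assumed prevalence of 5%, 10% or 20% this is 40%, 65% or 89%. So an imbalance could easily occur, but under these assumptions its effect on the mean is well below the difference the comparison could detect.

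**The case against.** The case on the other side has real force.

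- **Purpose of the criterion.** VII.A.1.h sits beside realistic expectations, vaccination and willingness to travel. It may be meant to secure suitability for elective surgery and about 1.5 years of follow-up, which controls do not face. That explains the asymmetry but does not remove its effect: whatever its purpose, the criterion selects one group on a factor that can affect the scores.
- **Existing safeguards.** Informed consent and the exclusion for inability should remove gross impairment. What is left is mild impairment, and the documents give neither an MMSE pass mark nor evidence that the screener would catch it. This limits the size of the problem, and of the benefit from the fix.
- **Localization.** A reader might infer that unscreened controls would also localize worse. The background section reports localization with CROS and bone-conduction devices at chance and no better than unaided, which leaves little room to worsen. The same section allows that long experience might change this, so an effect is not ruled out, but it is not established.
- **Percentage points.** A reader might work out that one or two impaired controls in 10, each scoring 10 to 20 points lower, would cut the control mean by 0.1 × 10 = 1 to 0.2 × 20 = 4 points. Apart from both inputs being assumed, this could fit only tests run under one fixed condition. In noise, VII.D steps the AzBio signal-to-noise ratio by performance and uses an adaptive ratio for BKB-SIN. A weaker listener stays at an easier level, so raw AzBio percentages need not fall by a fixed amount unless compared at the same ratio.
- **Net direction.** A reader might infer that Claim B.1 as a whole is biased toward the implant. Implant subjects must be dissatisfied with, or have stopped using, a current option, while controls have at least 12 months with theirs. With such other differences in play, this item alone does not settle the net direction. For the questionnaires, no direction is argued.
- **Analysis.** Section IX defines no between-group test, so the error rates in the working are not those of a planned analysis. That omission matters more to Claim B.1 than the missing screen does.

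**Conclusion.** The point holds as a minor, inexpensive matter of comparability. The two groups are selected differently on cognition, the plan cannot detect or correct an imbalance, and this could contribute bias toward the implant in the speech-perception part of Claim B.1. The size cannot be estimated from the documents. The 0.05 to 0.30 SD range depends wholly on the assumed share and deficit, and the true figure is probably modest.

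The reach is narrow. Claim B.1 serves a secondary aim of a study that describes itself as a feasibility study. The primary effectiveness endpoint (Section X.B, implant on versus off) and Claim B.2 (the same person with each device) are within-subject and are not touched. The documents do not support reading this as a demonstrated bias, as a localization effect, or as a threat to the primary result.

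**What to change.** Add the two parts of VII.A.1.h, "No reported cognitive issues" and "Pass the Mini Mental State Examination (MMSE) screener", to the control inclusion criteria in VII.B.1. Give the MMSE at the start of the single control visit, before the battery, with the same pass mark as for implant subjects, and record the result.

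For controls already tested without it, apply the first part from the clinical record and report Claim B.1 with and without those affected.

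The cost is a few minutes per control at an existing visit, and possibly one or two controls found ineligible. If two of 10 were lost and not replaced, the standard error against 16 implant subjects would rise from 0.403 to √(1/8 + 1/16) = 0.433 SD, so it is better to replace them. Treatment and the primary analysis do not change. The criterion removes the difference in selection on cognition; the other selection differences in Claim B.1 remain.

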Appendix A graphically depicts the timeline and associated measures

The Candidacy Evaluation and Preoperative Evaluation can either occur during the same visit or two different visits.

- 1. **Candidacy Evaluation.** This interval may overlap with the Preoperative Evaluation interval.
 - a. Audiologic Evaluation
 - i. Unaided air- and bone-conduction thresholds in both ears
 - a. Air-conduction assessed with inserts
 - ii. Unaided word recognition in both ears
 - a. Measured with recorded CNC words (50-word list)
 - b. Masking provided when appropriate
 - iii. Tympanometry in both ears
 - iv. Aided word recognition in the affected ear
 - a. Measured with recorded CNC words (50-word list)
 - b. Masking applied to the contralateral ear
 - v. Completion of the Tinnitus Handicap Inventory
 - vi. Determine if potential subject meets candidacy criteria
 - b. Medical Evaluation
 - i. Determine if potential subject is healthy enough to undergo cochlear implantation
 - ii. Associated imaging studies
 - a. This is standard of care for these patient populations
 - b. May also be completed at Preoperative Evaluation
 - iii. Discussion of alternative treatment options
 - iv. Determine if potential subject meets candidacy criteria
 - c. Informed Consent
 - i. Review and discussion of consent form
 - ii. Provide time for subject to review consent form and ask questions
 - iii. Provide subject with a signed copy of the completed consent form

2. **Preoperative Evaluation**. This interval may overlap with the Candidacy Evaluation interval.

The Preoperative Evaluation will be completed within 6 months of the surgery date.

- a. Audiologic Evaluation
 - i. Obtain a case history, including but not limited to:
 - a. Onset of hearing loss
 - b. Progression to moderate-to-profound sensorineural hearing loss
 - c. Suspected etiology of hearing loss
 - ii. Unaided air- and bone-conduction thresholds in both ears
 - a. Air-conduction assessed with insert phones
- iii. Unaided word recognition with CNC words in both ears
 - a. Measured with recorded CNC words (50-word list)
 - b. Masking provided when appropriate
- iv. Tympanometry in both ears
- v. Subjects will complete the test battery detailed in section VII.D.
 - a. Two listening conditions:
 - i. unaided
 - ii. bone-conduction test device or BAHA
 - a. The bone-conduction test device will be the Cochlear BAHA Intenso on a headband

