Subjects who utilize a hearing aid in the contralateral ear may continue to use this technology during the sound field test conditions where the contralateral ear remains open. Hearing aid output will be measured using NAL-NL1 targets.

- a. Aided thresholds with the external speech processor on will be measured using pulsed, warble tones
 - i. Frequencies assessed: 250-8000 Hz, including all inter-octaves
 - ii. Masking presented to the contralateral ear
- b. Speech Perception Measures

Recorded materials will be presented at 60 dB SPL.

- i. Speech Perception in Quiet
 - a. Listening condition
 - i. Speech 0° azimuth
 - b. Speech perception materials
 - i. CNC words
 - ii. AzBio sentences
- ii. Speech Perception in Noise
 - a. Listening conditions
 - i. Speech and noise 0° azimuth
 - ii. Speech 0° azimuth and noise to implanted side
 - iii. Speech 0° azimuth and noise to contralateral ear
 - b. Speech perception materials
 - i. AzBio sentences
 - a. If >50% at SNR+10, then SNR+5
 - b. If >50% at SNR+5, then SNR+0
 - ii. BKB-SIN sentences with adaptive SNR
- iii. Listening Conditions
 - a. Cochlear implant speech processor off
 - i. Contralateral ear only
 - b. Cochlear implant speech processor on
 - i. Cochlear implant + contralateral ear
- c. Localization
 - i. The stimulus is a 200-ms speech-shaped noise, presented at 70-dB SPL from one of the 11 speakers (evenly spaced -180 to 180 degrees), selected at random
 - ii. The intensity level for each stimulus presentation will be randomly varied (10 dB around 70 dB SPL)
 - iii. The listener will be facing the center speaker during stimulus presentation. The task is to identify the source of the noise. No feedback is provided.
 - iv. Listening Conditions

- a. Cochlear implant speech processor off
 - i. Contralateral ear only
- b. Cochlear implant speech processor on
 - i. Cochlear implant + contralateral ear
- 4. Subjective questionnaires
 - a. Speech, Spatial and Qualities of Hearing Scale (SSQ), Gatehouse & Noble (2004)
 - b. Abbreviated Profile of Hearing Aid Benefit (APHAB), Cox & Alexander (1995)
 - c. Tinnitus Handicap Inventory, Newman, Jacobson & Spitzer (1996)
- E. Aural Rehabilitation

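### The tinnitus questionnaire is an entry cut-off for implant subjects only, so its planned comparison with controls cannot be read as a device effect (minor)

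*Combined protocol and SAP*

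**What the plan says.** **Entry, implant group (VII.A.2).** A candidate is excluded if the "Subject obtains a severe or catastrophic score on the Tinnitus Handicap Inventory". A second exclusion is "Tinnitus as the primary purpose for seeking cochlear implantation". The candidacy evaluation in VII.C.1, where eligibility is decided, includes "Completion of the Tinnitus Handicap Inventory".

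**Entry, control group (VII.B.2).** There are four exclusions: non-native English, conductive loss, a compromised auditory nerve, and "Inability to participate in test battery". None concerns tinnitus.

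**Outcome.** The THI is the third of three subjective questionnaires in the battery (VII.D.4). Implant subjects complete the questionnaires preoperatively and at 1, 3, 6, 9 and 12 months (Appendix A). Controls have "One evaluation interval to complete the test battery outlined in section VII.D" (VI.B.2), so they have no pre-device score.

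**Comparison.** Objective III.B.1 is to "Compare speech perception, localization, and subjective outcomes to a control group of implantable bone-conduction device recipients". Claim VIII.B reads "Cochlear implantation provides similar or superior speech perception, localization, and/or quality of life as compared to that found with bone-conduction devices", and VIII.B.1 lists the control-group comparison as one of its two supports.

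**Analysis.** Section IX specifies within-subject repeated-measures ANOVA at p ≤ 0.05. It gives no between-group model, baseline adjustment, matching or restriction for any outcome.

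**The concern.** Small, unmatched control groups always differ from the treated group in ways that cannot be measured. This case is more specific: the outcome scale is itself a selection variable, and in one group only. Implant subjects enter with the top of the THI range removed, and controls enter with the whole range. A lower mean THI in the implant group at 12 months would therefore arise in part from eligibility.

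The parts of claim B are joined by and/or, so a favourable subjective result could be cited by itself. Nothing in Section IX would stop a lower implant mean on this questionnaire from being cited in that way. Controls are measured once, after their device, so a between-group comparison of change from baseline cannot repair the problem.

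**Working it through.** **Inputs from the documents.** 20 implant subjects (VII.A.3), at least 10 controls (VII.B.3), about 20% dropout (Section IX), significance at 0.05 (IX.B).

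**The plan's own figure.** 20 × (1 − 0.20) = 16 implant completers. The sample of 20 cannot be checked further, because Section IX gives no effect size, SD or power, and it gives no calculation for the group comparison.

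**Assumed, because the documents do not give them.** Higher THI means greater handicap; scores are normal; both groups come from the same source population; the device has no effect. The share q of candidates above the cut-off is 5-30%. The correlation r between the entry and 12-month scores is 0.5-0.9. The test is a two-sided t-test.

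**Step 1: shift in the implant mean.** With c the normal quantile at 1 − q, the shift in population SDs is −r × φ(c)/(1 − q).

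| q | φ(c)/(1 − q) | shift, r = 0.5 | shift, r = 0.9 |
|---|---|---|---|
| 5% | 0.109 | −0.05 | −0.10 |
| 10% | 0.195 | −0.10 | −0.18 |
| 20% | 0.350 | −0.18 | −0.32 |
| 30% | 0.497 | −0.25 | −0.45 |

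**Step 2: false significant result favouring the implant (nominal 2.5%).** 20,000 simulated trials per setting; each range runs from r = 0.5 to r = 0.9.

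| q | 16 vs 10 | 20 vs 10 |
|---|---|---|
| 5% | 3.5-4.1% | 3.4-4.5% |
| 10% | 4.5-6.7% | 4.4-7.6% |
| 20% | 6.5-13.8% | 6.9-15.6% |
| 30% | 9.1-23.6% | 9.7-27.0% |

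Across these settings the implant mean is the lower one in 55-89% of trials, against 50% if the comparison were fair.

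**Step 3: how much would cancel it?** Suppose the implant candidates' source population has a THI worse than the controls' by d SD, and q is now the share of the control population above the cut-off. The two effects cancel when d = r × φ(c − d)/Φ(c − d). For r from 0.5 to 0.9 this gives d of 0.06-0.12 (q = 5%), 0.12-0.25 (10%), 0.23-0.57 (20%) and 0.34-1.03 (30%).

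**Step 4: would the same cut-off applied to controls repair it?** Their only score is the post-device outcome, so their mean would fall by the full φ(c)/(1 − q), while the implant mean falls by r times that. The remaining difference is (1 − r) × φ(c)/(1 − q), now against the implant. For q = 10, 20 and 30% this is 0.04, 0.07 and 0.10 SD at r = 0.8, and 0.10, 0.18 and 0.25 SD at r = 0.5.

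**The case against.** **Direction.** A reader might infer that the comparison favours the implant. The documents do not support that as a net statement. Implant subjects must be dissatisfied with, or have stopped using, an existing option (VII.A.1.d). Controls must have at least 12 months on their device, with no dissatisfaction requirement (VII.B.1.b). How these differences affect THI is unknown, and Step 3 shows that a modest difference could cancel the shift when few candidates are cut off. This objection stands. It does not rescue the comparison, because an offset of unknown size is not a safeguard.

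**No named test.** No section specifies a between-group THI test. The THI enters through the general reference to subjective outcomes in III.B.1, and VIII.B speaks of quality of life. Including it is a fair reading of VII.D.4, but the error rates above belong to a t-test supplied for illustration. This also stands.

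**Size.** A reader might take the upper end as the expected error rate. It needs 30% of candidates cut off and a correlation of 0.9 together. At 5% cut off and a correlation of 0.5 the rate is 3.5%, close to nominal.

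**Importance.** This is one of three questionnaires, within a secondary aim of a feasibility study. Claim B also has a within-subject support (VIII.B.2), and the primary on-versus-off endpoint (X.B) does not use controls. This stands and limits the severity.

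**Conclusion.** The concern holds as a minor point. The THI is an entry criterion in one group and an outcome in both, and Section IX has nothing that removes the imbalance. With all else equal, the criterion lowers the implant mean by about 0.05-0.45 SD. It raises the chance of a false finding for the implant to about 3.5-24%, against a nominal 2.5%, with 16 completers and 10 controls. These ranges rest on an assumed excluded share, correlation, normal scores, a common source population and a t-test; none of these is in the documents. The net direction after all selection differences is unknown, so a group difference in THI in either direction, or its absence, cannot be attributed to the device.

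**What to change.** Add to Section IX: the THI is analysed only as within-subject change from the preoperative score. It is not used in the comparison with controls or as support for claim B. Control THI scores are reported descriptively, with the eligibility difference stated. The baseline has to be named, because IX.B.3 refers only to the post-activation intervals.

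Do not restrict controls to those below the cut-off on their single post-device score. That selects on the outcome, reverses the shift (Step 4), and can hide a real difference.

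One detail to settle: VII.C lets the candidacy and preoperative evaluations share a visit, so the screening score could also serve as the baseline. If it does, regression to the mean raises the later scores by (1 − r) × φ(c)/(1 − q) SD, the same expression as in Step 4. That is 0.1 × 0.109 = 0.01 SD to 0.5 × 0.497 = 0.25 SD over the assumed ranges, in the direction of worse tinnitus. Section IX should say which score is the baseline and, if it is the screening score, note this drift. It cannot create an apparent benefit.

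The cost is a few sentences. One secondary between-group questionnaire comparison is given up. The scores are already scheduled, and the primary endpoint and all other control comparisons are unchanged.
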